4.8 Compliance with intervention

A CACE analysis for the outcome of birth weight will be used to obtain an unbiased estimate of the effect of the intervention with full compliance (defined as the participant being found to be a biochemically verified non-smoker at late pregnancy). An instrumental variable model will be used, using the compliance variable as the endogenous variable, and treatment group, the age, height and weight of the mother at booking, years of smoking, income status, level of smoking (as measured by the Fagerström score), whether the engagement data was collected before the 16th of March 2020, and centre as exogenous variables.

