2.2 Design

CPIT III is a phase III, pragmatic, multi-centre, randomised controlled trial of the offer of financial incentives added to usual SSS care to engage with SSS and quit smoking versus usual care alone. In addition, economic and process evaluations were embedded in the study.

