2.3 Intervention

2.3.1 Original intervention

The intervention was composed of several stages, each of which involved the offer of a financial incentive in the form of a Love2shop gift voucher, delivered via registered post.

The first stage of the intervention was designed to encourage participants to engage with SSS, while the remaining stages were designed to encourage participants to quit smoking and remain abstinent.

At the first stage, if the participant attended an appointment with the SSS and set a date on which they would quit smoking, they received a gift voucher with a value of £50.

At the second stage, the smoking status of those participants who engaged with SSS and set a quit date was obtained from the SSS at four weeks post-quit date. Smoking status was ascertained by asking the participant the question:

1. Have you smoked (even a puff) in the last two weeks?

Participants who answered 'No' were contacted by a research nurse to arrange an appointment to obtain a Carbon Monoxide (CO) breath test reading, where this had not already been collected by the SSS. Participants who had a CO reading less than or equal to the accepted threshold for their site received a gift voucher with a value of £50. Table 1 gives details of the CO threshold for each site.

Table 1: CO threshold for each site

Site	CO threshold (<=ppm)
Lanarkshire	4
Belfast	3
Salisbury	4
Poole	4
Isle of Wight	5
Dorchester	4
Portsmouth	4

At the third stage, the smoking status of those participants, who met the criteria to receive a shopping voucher at the second stage, was obtained from the SSS (where available) or by a research nurse at 12-weeks post quit date. Smoking status was obtained by asking the participant the question:

1. Have you smoked at all since your one-month follow-up?

Participants who answered 'No' were contacted by a research nurse to arrange an appointment to provide a CO breath test reading, where this had not already been collected by the SSS. Participants who had a CO reading less than or equal to the accepted threshold for their site received a gift voucher with a value of £100.

At the fourth stage, participants were contacted by the trial team at a random date between 34 and 38 weeks gestation, regardless of whether or not they met the criteria for the previous shopping vouchers. The participants were asked the following questions:

- 1. Have you smoked at all in the last eight weeks?

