2.3.2 Changes to the intervention in response to the Covid-19 pandemic

Due to the Covid-19 pandemic, SSS were disrupted. As a result, on the 16th of March 2020 the following changes were made for the intervention group:

- Participants who received SSS behavioural support and set a quit date via telephone (where this would have previously been conducted face-to-face) were considered to have engaged with the SSS, and received a gift voucher with the value of £50.
- Participants who self-reported as having quit with no CO verification at the 4-week follow-up received a gift voucher with the value of £50.
- Participants who self-reported as having quit at the 4-week follow-up were contacted at the 12 week follow-up. If they self-reported as quit with no CO verification at the 12-week follow-up they were sent a gift voucher with the value of £100.
- Participants who self-reported as having quit at the primary outcome stage in late pregnancy and for whom a saliva sample was received by the trial team were sent a gift voucher with the value of £200.

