2.5 Outcomes

2.5.1 Primary Outcome

The primary outcome is cotinine/anabasine verified abstinence from smoking for at least 8 weeks towards the end of pregnancy. All participants were contacted by the Trial Team at a random date between 34 and 38 weeks gestation and asked the following questions:

- 1. Have you smoked at all in the last eight weeks?
- 2. If yes, have you smoked more than five cigarettes in total in the last 8 weeks?

If the participant answered 'No' to the first question, or 'Yes' to the first question and 'No' to the second question, they were contacted by a research nurse to arrange an appointment to biochemically verify their smoking status. Participants were asked to provide a CO reading and a saliva sample (or urine sample when saliva collection could not be tolerated), which was tested for cotinine in the first instance. Where the cotinine result was less than or equal to the threshold (Table 2) and the participant had not reported any NRT/e-cigarette use then the participant was defined as a biochemically verified non-smoker.

Participants who indicated current NRT/e-cigarette use and had a saliva cotinine result < 10ng/ml were defined as biochemically verified non-smokers. Where participants indicated current NRT/e-cigarette use and the saliva cotinine result was \geq 10ng/ml, saliva samples were also tested for anabasine. Where the anabasine result was less than or equal to the threshold 0.2ng/ml and the saliva cotinine result was \geq 10ng/ml then the participant was defined as a biochemically verified non-smoker.

Urine samples were also collected from participants who indicated NRT/e-cigarette to allow further assaying in the event of any dubiety. At present however there is no defined threshold for anabasine in urine and a judgement regarding smoking status would need to be taken by the Research team in conjunction with advice from ABS Labs in this scenario.

Table 2: Thresholds for cotinine samples in saliva

Cotinine threshold, ng/ml	
Saliva	10.0
Urine	50.0
Plasma	10.0

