2.9.4 Follow-up 4: Late pregnancy (34-38 weeks gestation)

All participants were followed up at the primary outcome stage in late pregnancy. Follow-up telephone contact was attempted by the trial contact centre at a random date between 34 and 38 weeks gestation allocated at the time of initial randomisation. Trial research nurses reviewed participants' notes one week prior to the telephone contact to check the health status of mother and baby and alert TCC staff to any adverse events e.g. miscarriage or stillbirth, that required particular sensitivity when conducting follow-up. TCC staff were blind to group allocation.

Three attempts were made by the TCC to contact women. If no contact was established, local research staff followed up women by telephone, text, and letter. On successful contact, women were asked: 'Have you smoked in the last 8 weeks?' If yes, 'Have you smoked more than 5 cigarettes in that time?'. EQ-5D-5L data, and current NRT/electronic cigarette use were also collected at this time point.

Self-report of not smoking was corroborated by cotinine estimation on saliva or urine (when saliva collection could not be tolerated). Where women were using NRT or e-cigarettes, anabasine assay on saliva was also conducted. Cotinine and anabasine were assayed by ABS Laboratories Limited (https://www.acmgloballab.com/about-us/our-locations/europe-london-uk). To minimise the potential for women to 'game' the primary outcome, incentive payments were dependent on the CO result, which is an immediate measure, and not on the cotinine or anabasine level.

An important aspect of the primary outcome for this phase III trial is the proportion of women successfully followed up in both the intervention and control group. To minimise loss to follow-up, particularly among controls, women in both groups will receive Love2Shop vouchers of £50 and £25 for providing data and saliva/urine samples where applicable at the primary (late pregnancy) and secondary (six months post-partum) outcome time points respectively (Figure 2.).

To assess if a) women lost to trial follow-up are still smoking towards the end of pregnancy, and b) the primary outcome has been 'gamed' (saliva cotinine below the cut-off but still smoking in late pregnancy) residual blood from routine late pregnancy samples, where available, will be tested.

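### The birth-weight CACE is mislabelled: it can estimate only the effect of verified abstinence in women who abstain because of the offer, and only under assumptions the SAP does not state

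*SAP*

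**What the plan says.** SAP section 4.8 plans an instrumental variable model for birth weight that "will be used to obtain an unbiased estimate of the effect of the intervention with full compliance". Compliance is "defined as the participant being found to be a biochemically verified non-smoker at late pregnancy". The model is specified as "using the compliance variable as the endogenous variable, and treatment group", followed by maternal and smoking covariates, a Covid-period indicator and centre, all listed together as exogenous.

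Other sections define the pieces differently:

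- Section 2.5.1: "The primary outcome is cotinine/anabasine verified abstinence from smoking for at least 8 weeks towards the end of pregnancy". The compliance variable is therefore the primary outcome.
- Section 2.2 describes the trial as a "randomised controlled trial of the offer of financial incentives added to usual SSS care". What is randomised is an offer.
- Section 2.3.1, on the opening payment: "if the participant attended an appointment with the SSS and set a date on which they would quit smoking, they received a gift voucher". This payment does not require quitting.
- Section 2.3.2, from 16 March 2020: "If they self-reported as quit with no CO verification at the 12-week follow-up they were sent a gift voucher with the value of £100".
- Section 2.9.4, late pregnancy: "incentive payments were dependent on the CO result, which is an immediate measure, and not on the cotinine or anabasine level".

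Section 4.4 counts a missing primary outcome as smoking. Sections 2.9.4 and 4.9 foresee that some women who test as non-smokers will have gamed the outcome. Section 4.8 states no exclusion restriction and no monotonicity assumption, and no sensitivity analysis is planned for this model.

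**The concern.** Full compliance with an intervention normally means taking it up. Here it means achieving the result the intervention is meant to produce, and the two come apart in both arms. A usual-care woman who quits counts as a complier with something she was never offered. A woman in the incentives arm can receive every voucher (50 + 50 + 100 + 200 = £400) and still be a non-complier, because no payment depends on the cotinine or anabasine result.

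A reader who takes section 4.8 at its word would report the estimate as the birth-weight benefit of the voucher scheme when fully taken up, and would believe it free of bias. Neither follows from the model described.

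**Working it through.** **Inputs from the SAP.** Quit rates 7% and 14%, 90% power, 15% loss, 470 per arm (section 2.6); two-sided 5% (section 4.1).

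**The plan's own figure.** The SAP gives no figure for the CACE, so the design rates are checked through the sample size. The usual two-proportion formula with pooled variance under the null gives 401 per arm; 401/0.85 = 472, or 944 in total. Unpooled variance gives 398, then 469 per arm, or 938 in total. The stated 940 reproduces.

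**What the model estimates.** Leaving covariates aside, the estimate is

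CACE = (difference in mean birth weight) / (difference in verified quit rate).

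The denominator at the design rates is 0.14 − 0.07 = 0.07, so the CACE is 1/0.07 = 14.3 times the intention-to-treat difference (20 times at a 5-point difference, 10 times at 10 points). That scaling is proper if the target is the effect of quitting. It misleads if the result is read as the effect of the intervention.

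**Effects outside verified quitting.** Any average birth-weight effect of the offer by another route enters the numerator only. Each 1 g adds 14.3 g. An assumed 10 g adds 10/0.07 = 143 g. The SAP gives no size for such an effect, so 10 g is illustrative.

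**Direction.** Hold the observed verified difference at 7 points. Let q be the excess, in points, of incentives-arm women whose smoking falls without verified quitting; r their birth-weight benefit relative to a true quitter; and g the excess, in points, of falsely verified women, taken to gain nothing. Then

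CACE / true effect of quitting = (7 + q·r − g) / 7.

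All three are assumptions.

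| q | r | g | Ratio |
|---|---|---|---|
| 2 | 0.5 | 0 | 1.14 |
| 5 | 0.5 | 0 | 1.36 |
| 7 | 1 | 0 | 2.00 |
| 0 | – | 1 | 0.86 |
| 0 | – | 2 | 0.71 |
| 2 | 0.5 | 1 | 1.00 |
| 1 | 0.5 | 2 | 0.79 |
| 5 | 0.5 | 1 | 1.21 |

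**Instrument strength and precision, unadjusted.** SE of the quit difference = √((0.07×0.93 + 0.14×0.86)/470) = 0.01987, so F = (0.07/0.01987)² = 12.4. With 470×0.85 = 399.5 per arm, F is 10.6. For an assumed birth-weight SD of 0.55 kg, the SE of the birth-weight difference is 0.55×√(2/470) = 0.0359 kg. Dividing by 0.07 gives 0.513 kg, and the 95% half-width is 1.96×0.513 = 1.0 kg (0.91 to 1.10 kg for an SD of 0.50 to 0.60). This treats the denominator as known and ignores covariate adjustment.

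**The case against.** The best defence is that the compliance definition stands in the same sentence as the label, so a careful reader knows what was meant, and that this is one supplementary analysis of a secondary outcome. Both points are fair. They limit the consequence but do not make the label or the claimed property correct.

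Several stronger readings are tempting, and the documents do not support them:

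- *The estimate is certainly inflated.* The other routes push it up only if they raise birth weight, and the SAP gives no size for them. Gaming, if commoner with incentives, enlarges the denominator and pulls the estimate down. For example, if 15% of quits went unverified in both arms (an assumption; the 15% in section 2.6 is loss to follow-up), the denominator would fall from 7 to 5.95 points and inflate the estimate by 18%. An excess of 1.05 points of falsely verified women would restore the denominator.
- *The model is not identified because treatment group is listed with the covariates.* Excluded instruments are exogenous variables in the usual terminology, and treatment group is evidently the instrument intended. This is a gap in wording.
- *Quitting in usual care invalidates the method.* It does not. Women who would quit in either arm are accommodated under monotonicity. Their presence shows that the label is wrong, not that the estimator fails.
- *Voucher money itself is a large direct route.* The £200 payment comes only at 34 to 38 weeks, and £150 of the rest was tied to abstinence at 4 and 12 weeks. Early quitting with relapse, cutting down and quits without a sample are the more credible routes.

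The F statistic and the interval width concern precision. They do not establish bias, but they bear on how the result should be reported.

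**Conclusion.** Wrong as written, on two counts. The quantity is not the effect of the intervention under full take-up. It is at most the effect of verified late-pregnancy abstinence on birth weight in women who abstain because of the offer. The property claimed is also wrong: an instrumental variable estimate is at best consistent, and here only under an exclusion restriction and monotonicity that the SAP does not state. The SAP's own voucher schedule makes the exclusion restriction doubtful.

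The firm figure is the multiplier of 14.3 on any effect outside verified quitting, which rests only on the planned 7-point difference. The ratios in the mixed cases, 0.79 to 1.21, rest on assumed inputs and show that the net direction is open. Nothing here touches the primary analysis or the intention-to-treat analysis of birth weight in section 4.5.

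**What to change.** In section 4.8:

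1. Delete the word unbiased and the description of the result as the intervention's effect under full compliance.
2. State the estimand as the effect of verified late-pregnancy abstinence on birth weight among women who abstain because of the offer. State the exclusion restriction and monotonicity beside it.
3. Note both directions of possible bias: upwards from other routes that raise birth weight, downwards from gaming that is commoner in the incentives arm.
4. Name treatment group as the sole excluded instrument, and the remaining variables as covariates in both stages.
5. Report the first-stage F and an Anderson-Rubin interval, which remains valid when the instrument is weak.
6. If the model is repeated with self-reported quitting as the exposure, present it only as a bracket. Section 4.7.2 itself anticipates over-reporting in the incentives arm, so it cannot serve as a correction.

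The cost is a few sentences, one extra statistic and one interval, plus a further run if step 6 is taken up. If the SAP is already final, the departure form in section 1.3.2 is the place to record the change. The downside is a less favourable claim for this one analysis.

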2.6 Sample size

The aim was to recruit 940 participants to the trial (470 per arm). This gave 90% power to detect a doubling of the smoking cessation rate from 7% to 14%, allowing 15% loss to follow-up. The smoking cessation rate in the control group was derived from the smoking cessation rate found in the feasibility trial [2], and two other large trials of smoking cessation interventions in pregnant smokers [3, 4]. The smoking cessation rate in the intervention group was derived from the cessation rate in the feasibility trial, along with considerations of the effect size that would be considered clinically important.

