4.1 Strategy for reporting data and general considerations

Data will be analysed and reported according to CONSORT guidelines [5]. A CONSORT diagram will be produced (see Figure 2). Analyses will be conducted using Stata version 16 or later [6]. The version of Stata to be used will be confirmed in the final report. All analyses will be conducted following the principle of intention-to-treat unless stated otherwise. Statistical tests will be two-sided at the 5% significance level. Effect size estimates will be presented with 95% confidence intervals.

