4.5 Secondary outcome analyses

Engagement with SSS will be analysed using a mixed-effects logistic regression model adjusting for treatment group, age, years of smoking, income status, level of smoking (as measured by the Fagerström score) and whether the engagement data was collected before the 16th of March 2020, with centre as a random effect.

CO-validated smoking status at 4 weeks post-quit date will be analysed using a mixedeffects logistic regression model, adjusting for treatment group, age, years of smoking, income status, level of smoking (as measured by the Fagerström score) and whether the CO-validated smoking status was collected before the 16th of March 2020, with centre as a random effect. If a participant is missing their smoking status, it shall be assumed the participant is smoking.

Birth weight will be analysed using a mixed-effects linear regression model, adjusting for treatment group, the age, height and weight of the mother at booking, years of smoking, income status, level of smoking (as measured by the Fagerström score) and whether the birthweight data was collected before the 16th of March 2020 as fixed effects, and centre as a random effect. If a participant is missing data on birth weight, it shall be assumed the data is missing at random conditional on the covariates included in the analysis model [13, 14].

Continuous and point abstinence outcomes obtained at six months postpartum will be analysed using mixed-effects logistic regression adjusting for the same covariates and applying the same assumptions used in the primary outcome analysis (with the exception that whether the postpartum point abstinence outcome was collected before 16th of March 2020 will be adjusted for instead of adjusting for whether the primary outcome was collected before the 16th of March 2020). If a participant is missing their smoking status, it shall be assumed the participant is smoking. Participants who at postpartum were followed up earlier than 6 months will be excluded from the analysis of continuous and point abstinence

outcomes obtained at six months postpartum, and will be accounted for in a sensitivity analysis.

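### SAP 4.8 treats the primary outcome as compliance and claims an unbiased effect of the intervention, which the model does not give; its date covariate also disagrees with 4.5

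*SAP*

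**What the plan says.** Section 4.8 plans a CACE analysis of birth weight, "used to obtain an unbiased estimate of the effect of the intervention with full compliance". Full compliance is "defined as the participant being found to be a biochemically verified non-smoker at late pregnancy". The compliance variable is endogenous. Treatment group, maternal and smoking covariates, a date indicator and centre are listed as exogenous. No instrumental-variable assumption is stated, and no sensitivity analysis for one is planned.

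Section 2.5.1 gives the same event as the trial's main endpoint: "The primary outcome is cotinine/anabasine verified abstinence from smoking for at least 8 weeks towards the end of pregnancy".

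The intervention (section 2.3.1) is a staged offer: £50 for engaging with the Stop Smoking Service and setting a quit date, £50 for abstinence at four weeks, £100 at 12 weeks and £200 in late pregnancy. The late-pregnancy stage is open to all incentives-arm women, whether or not they earned the earlier vouchers. Under section 4.4, a woman with no primary outcome counts as a smoker.

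On the Covid-19 date indicator, section 4.8 uses "whether the engagement data was collected before the 16th of March 2020". The birth-weight model in section 4.5 uses whether "birthweight data was collected before the 16th of March 2020 as fixed effects".

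**The concern.** A complier analysis normally asks what the treatment does in those who take it up. Here compliance is the result that the treatment is meant to produce. At the planned control rate, 0.07 × 470 = about 33 control women would comply with an offer never made to them. An incentives-arm woman who engaged, was confirmed abstinent at four and 12 weeks and then relapsed would be non-compliant. The fitted quantity is therefore an effect of verified quitting, not of the intervention.

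That quantity is identified only if the offer changes birth weight through verified late-pregnancy abstinence and by no other route. The vouchers separately reward engagement and earlier abstinence. Women who cut down, who quit and relapsed, or who quit but gave no sample may have heavier babies while coded as non-compliers.

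At stake is a figure in grams reported as an unbiased effect of the intervention when it is neither, and fitted with a different date covariate from the intention-to-treat model that it accompanies.

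**Working it through.** **1. The planned first stage.** Section 2.6 states: "This gave 90% power to detect a doubling of the smoking cessation rate from 7% to 14%, allowing 15% loss to follow-up". It also states: "The aim was to recruit 940 participants to the trial (470 per arm"). Section 4.1 sets the test: "Statistical tests will be two-sided at the 5% significance level".

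- Pooled-variance formula: 401 per arm; 401/0.85 = 472; total 944.
- Unpooled formula: (1.960 + 1.282)² × (0.07 × 0.93 + 0.14 × 0.86)/0.07² = 398 per arm; 398/0.85 = 469 after rounding up; total 938.

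Both agree with 940, so a 7-point difference in verified abstinence is a fair planning value for the denominator.

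**2. The multiplier.** Without covariates, the estimate is

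IV = (arm difference in mean birth weight) / (arm difference in verified abstinence).

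With a denominator of 0.07, any contribution to the numerator is multiplied by 1/0.07 = 14.3, including one that bypasses verified abstinence.

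**3. Direction and size.** The SAP gives no rates for the mechanisms below, so all inputs beyond 7% and 14% are assumptions. Take a true effect of quitting of 200 g, so that the 7 points of extra true quitting contribute 0.07 × 200 = 14 g to the numerator. Let a further share q of women change their smoking because of the offer without being verified, each with a fraction f of the benefit.

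| Assumed mechanism | Calculation | Estimate | Ratio to 200 g |
|---|---|---|---|
| q = 2%, f = 0.25 | (14 + 1)/0.07 | 214 g | 1.07 |
| q = 5%, f = 0.25 | (14 + 2.5)/0.07 | 236 g | 1.18 |
| q = 10%, f = 0.25 | (14 + 5)/0.07 | 271 g | 1.36 |
| q = 10%, f = 1 | (14 + 20)/0.07 | 486 g | 2.43 |
| 15% of quitters unverified, both arms | 14/(0.07 × 0.85) | 235 g | 1.18 |
| Gaming by 1% of incentives arm | 14/0.08 | 175 g | 0.88 |
| Gaming by 3% of incentives arm | 14/0.10 | 140 g | 0.70 |
| Quitters verified: 95% incentives, 75% control | 14/(0.14 × 0.95 − 0.07 × 0.75) = 14/0.0805 | 174 g | 0.87 |
| q = 5%, f = 0.25, with 2% gaming | 16.5/0.09 | 183 g | 0.92 |
| q = 10%, f = 0.25, with 3% gaming | 19/0.10 | 190 g | 0.95 |
| q = 5%, f = 0.25, with 95%/75% verification | 16.5/0.0805 | 205 g | 1.02 |

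The downward mechanisms come from the SAP itself. Section 4.9 plans to measure gaming. Both arms receive £50 for late-pregnancy data and samples (2.9.4), but the £200 voucher, which depends on a saliva sample, is offered only in the incentives arm (2.3.1, 2.3.2).

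**4. Finite samples.** The approximate first-stage F is 0.07²/[(0.0651 + 0.1204)/m], with m women per arm. This is 10.6 at m = 399.5 (15% loss) and 12.4 at m = 470. Even with every assumption met, an instrumental-variable estimator is consistent, not exactly unbiased.

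**5. The covariate.** The other covariates in 4.8 and 4.5 match: age, height, weight, years of smoking, income status, Fagerström score and centre (a random effect in 4.5). Only the date indicator differs. Engagement must occur before 26 weeks (2.5.2.1). A woman who reaches the 34-week contact therefore gives birth at least 34 − 26 = 8 weeks after engaging. Women whose engagement data were collected before 16 March 2020 and birth-weight data after it are coded differently in the two models. The amendment log, which names 4.8 among the sections changed, describes the indicator as relating to when the outcome was collected. That suggests the intent, but the inconsistency rests on the two current sections.

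**The case against.** Section 4.8 states its compliance definition openly, so a careful reader can see what is estimated, and the effect of quitting on birth weight is a legitimate target. Treatment group is the only randomised variable in the exogenous list, so the instrument can be identified. The SAP gives no rate of relapse, cutting down or unverified quitting, so failure of the exclusion condition is not demonstrated. Only one binary covariate differs. The analysis supplements a secondary outcome and cannot alter the primary conclusion.

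Much of this stands. The exclusion condition is doubtful and untestable from the documents, not shown to fail, and one differing indicator does not make the two birth-weight models incomparable. None of it supports the word unbiased or the description of the estimand.

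A reader might also infer that the estimate is inflated. The documents do not support that: the upward scenarios are assumed, and gaming and unequal reward for samples act the other way.

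A reader might want compliance redefined as engagement with the Stop Smoking Service. That has the same weakness. A woman who never engages can still earn the late-pregnancy voucher, so the offer can act outside engagement, which is itself a trial outcome and open to controls as usual care.

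**Conclusion.** The point holds as a mislabelled estimand, an unsupported claim of unbiasedness and one inconsistent covariate. The model targets the effect of verified late-pregnancy abstinence on birth weight in women whom the offer induced to quit. That reading needs the exclusion condition, and monotonicity: no woman fails to be verified abstinent because of the offer when she would have been without it.

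At the planned 7-point first stage, effects outside that path are multiplied by about 14. Under the assumed inputs, single mechanisms move the estimate to between 0.70 and 2.43 times the true effect, and the three combinations shown give 0.92 to 1.02. Neither the net direction nor the size of bias can be fixed from the SAP. The effect of the covariate mismatch cannot be quantified either, because the number of women coded differently is not given.

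**What to change.** In section 4.8:

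- Relabel the analysis as an instrumental-variable estimate of the effect of verified late-pregnancy abstinence on birth weight. For clarity, say that allocation is the instrument.
- Delete the word unbiased and the description of the result as the effect of the intervention under full compliance.
- State the exclusion and monotonicity assumptions, and that bias may be in either direction: upward from earlier, partial or unverified quitting, downward from gaming or better sample return in the incentives arm.
- Replace the engagement-date indicator with the birth-weight-date indicator used in 4.5.

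The cost is a few sentences and one variable in one model, with no new data. The downside is a weaker claim for a supplementary analysis of a secondary outcome.
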